9.5. Variables

- i. myAIRVO 2 electronic monitoring data (device usage)
- ii. Number of exclusions
- iii. Number of withdrawals
- iv. Domiciliary oxygen use
- v. Aspects of myAIRVO 2 use
- vi. Clinical outcomes

9.6. Measurements

- i. myAIRVO 2 electronic monitoring
- ii. 30 day NHF therapy Diary
- iii. NHF therapy Questionnaire
- iv. Recording of events: myAIRVO 2 use, exclusions, withdrawals, and clinical outcomes
- v. Spirometry

9.7. Equipment

- i. Case report forms and questionnaires will be in paper format.
- ii. Spirometry data will be collected using a handheld spirometer (Jaegar pneumotac spirometer with J-Lab software)
- iii. De-identified data (Participant ID only) will be recorded on the CRFs will be scanned to Fisher and Paykel, who will then enter it onto a secure electronic study database.

9.8. Inclusion / Exclusion criteria

Participants will be 18 years of age or older

Participants will be admitted to the respiratory ward(s) of either recruiting hospitals with AECOPD as the primary diagnostic reason for admission. They will be excluded if:

- i. They are given a new domiciliary oxygen prescription during the current hospital admission
- ii. The investigator believes the participant or their care giver will be unable to safely use myAIRVO 2 device following discharge
- iii. They have any other condition which, at the investigator's discretion, is believed may present a safety risk or impact the feasibility of the study or the study results

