8.2. Objectives

The objectives of the study:

1. To estimate the duration of use of the device including the mean hours of use per day and number of days use, to inform an daily myAIRVO 2 prescription for the proposed randomized controlled trial
2. To estimate the proportions of potential participants who could proceed to the proposed randomized controlled trial
3. To estimate the proportions of potential participants who would require oxygen delivery through myAIRVO 2 in the proposed randomized controlled trial
4. To estimate aspects of the use of myAIRVO 2 after discharge and to in particular estimate patient ratings of ease of use, and the proportion of those who required changes to initial settings of temperature and flow, and the magnitude of these changes, to inform prescription design for the proposed randomized controlled trial
5. To estimate particular clinical outcomes relevant to the planned randomized controlled trial, including hospital readmission, Emergency Department (ED visit) and General Practitioner (GP) visit rates.

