9.4. End Points

The following end points will be evaluated:

Primary outcome:

The primary outcome will be NHF use for 30 days following discharge after AECOPD. Use will be expressed as hours of myAIRVO 2 use per day over 30 days, as obtained by myAIRVO 2 electronic monitoring.

Secondary outcomes:

Other use variables:

- i. Number of days of use, adjusted for number of days with myAIRVO 2 at home
- ii. Average use per day of myAIRVO 2 during week 1, week 2, week 3 and week 4.
- iii. Average use per day on days of myAIRVO 2 use

Withdrawals and exclusions:

- i. Proportion of participants screened that were excluded
- ii. Reason for exclusion
- iii. Proportion of participants enrolled that were withdrawn
- iv. Reason for withdrawal

Participants requiring oxygen delivery via myAIRVO 2:

- i. Proportion of participants using domiciliary oxygen

Aspects of myAIRVO 2 use:

- i. Proportion of participants who reported having reduced myAIRVO 2 flow settings from the initial flow
- ii. Reduction in flow
- iii. Proportion of participants who reported having increased myAIRVO 2 flow settings from the initial flow
- iv. Increase in flow
- v. Proportion of participants who reported having reduced myAIRVO 2 temperature setting from the initial setting
- vi. NHF therapy Questionnaire results

Clinical outcomes

- i. Proportion of participants with at least one hospital readmission within 30 days of discharge
- ii. Reasons for hospital admissions (AECOPD, other respiratory cause or other cause)
- iii. In those that had at least one hospital readmission:
 - a. Number of readmissions
 - b. Time to first hospital readmission
 - c. Hospital readmission length
- iv. Proportion of participants with at least one ED visit within 30 days of discharge
- v. Reason for ED visits (AECOPD, other respiratory cause or other cause)
- vi. In those that had at least one ED visit:
- vii. Number of ED visits
- viii. Time to first ED visit
- ix. Proportion of participants with at least one GP visit within 30 days of discharge
- x. Reason for GP visits (AECOPD, other respiratory cause or other cause)
- xi. In those that had at least 1 GP visit within 30 days of discharge: number of GP visits
- xii. LACE Index for hospital admissions
- xiii. Lung function measurements (FEV₁, SVC_{in} and FVC) at day 1 and 31.

* An ED visit is counted if the patient went to ED for assessment and was not subsequently admitted to a hospital ward.

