9.10.6. Excluded participants

All participant exclusions will be documented on the Participant eligibility_screening log

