9.14. Foreseeable Complications

There are no foreseeable complications with recruitment or completion of the study in general. All units have already been prepared for trial. Complications relating to adherence to the study protocol and NHF therapy use are outcome measures of this study.

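### The non-safety limb of exclusion iii permits selection on expected outcome in a study meant to estimate use, withdrawal and eligibility for the later trial

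*Combined protocol and SAP*

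**What the plan says.** Section 9.8 has three exclusions.

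- Exclusion i concerns a new domiciliary oxygen prescription during the admission.
- Exclusion ii applies when "The investigator believes the participant or their care giver will be unable to safely use myAIRVO 2 device following discharge".
- Exclusion iii covers any other condition which the investigator, at discretion, believes "may present a safety risk or impact the feasibility of the study or the study results". It lists no conditions and neither names nor rules out expected poor adherence.

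The study's targets are set elsewhere.

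- The primary outcome in 9.4 is device use: "Use will be expressed as hours of myAIRVO 2 use per day over 30 days, as obtained by myAIRVO 2 electronic monitoring".
- Objective 2 in 8.2 is "To estimate the proportions of potential participants who could proceed to the proposed randomized controlled trial".
- Section 9.14 adds: "Complications relating to adherence to the study protocol and NHF therapy use are outcome measures of this study".

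Exclusions are tracked. Section 9.10.6 states that "All participant exclusions will be documented on the Participant eligibility_screening log". The secondary outcomes in 9.4 include "Proportion of participants screened that were excluded", followed by the reason for exclusion. Section 11.6 assigns all screened patients to the analysis of one endpoint only, labelled 2.b.i, which by its position is the proportion excluded. Every other endpoint is analysed in patients discharged with a device. Section 9.3 treats bias as not relevant to this study.

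**The concern.** A feasibility study should meet the patients the later trial will meet, including those who use the device little or stop early. A discretionary exclusion for likely effect on feasibility or results lets an investigator act, before discharge, on a guess about the quantities being estimated. Safety does not need this limb: it is covered by exclusion ii, the first limb of iii, the oxygen-saturation withdrawal rules (9.10.3, 9.10.5) and discretionary safety withdrawal (9.11).

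Two results are exposed. Mean hours of use is to inform the daily prescription for the randomized trial, and observed withdrawal will colour its drop-out allowance. Both could look better than they would in an unselected sample. The objective 2 proportion also becomes partly a record of investigator judgement at two sites, against a standard that is not written down and so cannot be reliably repeated.

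**Working it through.** **1. The plan's own figure.** Section 11.2 gives a minimum of 80 patients and 20% drop-out. 80 / (1 - 0.20) = 100, which equals 20 + 80 as planned. Nothing in this calculation depends on exclusion iii.

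**2. What the protocol supplies for sizing the effect.** It states no expected exclusion rate, hours of use or standard deviation. The inputs below are therefore assumptions, shown over a range.

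**3. Mean use.** Let f be the share of otherwise eligible patients removed under the non-safety limb, and k their mean use divided by the mean use M of those enrolled. Mean use in all otherwise eligible patients is M[(1 - f) + fk], while the study reports M. The relative error is

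1 / [(1 - f) + fk] - 1.

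For example, f = 0.10 and k = 0.5 gives 1 / 0.95 - 1 = +5.3%.

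| f | k = 0 | k = 0.5 | k = 1 | k = 1.25 |
|---|---|---|---|---|
| 5% | +5.3% | +2.6% | 0% | -1.2% |
| 10% | +11.1% | +5.3% | 0% | -2.4% |
| 20% | +25.0% | +11.1% | 0% | -4.8% |
| 30% | +42.9% | +17.6% | 0% | -7.0% |

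The error is upward only if f > 0 and k < 1. It is zero at f = 0 or k = 1.

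**4. One unfavourable case in hours (assumed).** Suppose enrolled patients average 6 h/day and those removed would have averaged 1 h/day. The true mean is 6 - 5f. For f = 5%, 10% and 20% this is 5.75, 5.5 and 5.0 h, against 6 h reported, an overstatement of 4%, 9% and 20%.

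**5. Drop-out (assumed).** Suppose 15% of enrolled patients drop out and 50% of those removed would have done. True drop-out is 15% + 35% × f, that is 16.8%, 18.5% and 22% for the same f, against 15% reported. On the basis of 11.2, obtaining 80 patients at 15% drop-out needs 80 / 0.85 = 94.1, so 95; at 22% it needs 80 / 0.78 = 102.6, so 103. The gap vanishes if the two drop-out rates are equal and reverses if those removed would have dropped out less.

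**6. Objective 2.** Here k does not matter. Each use of the limb moves a patient from able to proceed to excluded. With 100 enrolled and f = 5%, 10%, 20% or 30%, the otherwise eligible number about 105, 111, 125 or 143, of whom 5, 11, 25 or 43 are removed on this ground.

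**7. Visibility.** The log and the two exclusion endpoints show that patients were excluded. Nothing requires a use of iii to be coded as safety or as feasibility/results. Read literally, 11.6 also puts the reason for exclusion in the set discharged with a device, which contains nobody excluded at screening.

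**The case against.** The strongest reply is that the clause is ordinary wording in a protocol otherwise built to keep low users. Eligibility is broad, participants may stop the device without leaving the study (9.11), and everyone discharged with a device is analysed for use (11.6). Exclusion iii requires a condition and does not mention adherence. The study results also include spirometry, readmissions, ED and GP visits and a questionnaire, so a condition could be excluded because it prevents valid spirometry, with no bearing on hours of use. Exclusions and their reasons are logged and are endpoints. If the randomized trial used the same clause, the estimates would describe its population.

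Much of this stands. A reader might infer that the study selects its sample on its own outcome, that the limb can work only by removing expected low users, or that use is therefore overstated. The documents support none of these. The outcome is unobserved at screening, low use is not a stated ground, other routes are open, and there are no data on how often the limb will be used or on whom.

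The permission itself remains. A log cannot recover hours of use for patients never enrolled, the two limbs need not be recorded separately, and 11.6 leaves the reasons endpoint in the wrong set. The documents do not say that the randomized trial will adopt the clause, and an unlisted judgement would be hard to reproduce if it did.

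**Conclusion.** The point holds as a risk created by the wording. The non-safety limb of exclusion iii permits selection on expected outcome in a study whose targets are use, withdrawal and the share able to proceed. Mean use may be overstated and drop-out understated, but the documents fix neither amount nor direction. The range of -7.0% to +42.9% for mean use rests wholly on assumed f (5% to 30%) and k (0 to 1.25). The effect on objective 2 needs only that the limb is used. The logging and exclusion endpoints make the selection partly visible without correcting the use estimate, and 9.3 offers no further safeguard.

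**What to change.** 1. In 9.8, end exclusion iii after the reference to safety risk, leaving the safety limb as it is. Alternatively, replace the non-safety limb with a list of objective conditions intended for the randomized trial, for example ones that prevent outcome measurement.
2. In either case, record on the existing screening log which ground applied to each exclusion.
3. Amend 11.6 so that the reason for exclusion, as well as the proportion excluded, is analysed in all screened patients.

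The cost is a short protocol amendment and one extra field on a log already in use. A few participants with less complete or noisier data may enter; low use or early stopping among them is information the study is meant to collect. The list in the alternative to step 1 limits the loss where a condition would make an outcome unmeasurable. The planned N of 100 is unchanged.

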9.9. Point of Enrolment

Participants will be considered enrolled and part of the study population at the time the inclusion and exclusion criteria have been met on the first visit in hospital. This will be after the Consent Form has been signed by both the Participant and Study Investigator.

9.10. Patient Procedure

9.10.1. Flowchart

The flowchart of the study is shown in Appendix 1.

9.10.2. Interventions

a. Participants will be split into 2 groups (those on a domiciliary oxygen prescription at the time of study entry and those who are not) with both groups receiving NHF therapy by myAIRVO 2. Participants will be encouraged to use myAIRVO 2 as much as possible (day and night) each day without impacting on daily living activities. Participants who are prescribed domiciliary oxygen will use NHF therapy via myAIRVO 2 with supplemental oxygen delivered via the device (section 9.10.04).

b. Interventions will be initiated from the time the participant is enrolled in hospital, to aid familiarization and acclimatization, and used until 30 days following discharge. Note the day of discharge is defined as Day 0.

c. By default, NHF will be set at 25L/min at 37°C. However, all participants are able to lower the delivered temperature to 34°C. For participants without a domiciliary oxygen prescription they can also increase/decrease the flow rate (up to 30L/min or down to 20L/min). Participants who have domiciliary oxygen flow rates are fixed in order to deliver a more consistent concentration of oxygen to maintain oxygen saturation.

9.10.3. Pre-discharge assessments and training

- a.** Participants will be approached at least one day prior to expected discharge to ensure familiarity with NHF therapy prior to discharge. Written informed consent will be obtained (see participant information sheets and consent forms).
- b.** Demographic data collection will include: Date of birth, gender, year of COPD diagnosis, presence of alpha antitrypsin deficiency, other respiratory conditions, current medications, pack year history (a pack year is defined as twenty cigarettes smoked every day for one year, for a calculator see <http://smokingpackyears.com/>), LACE index score and if domiciliary oxygen is prescribed. The Investigator will update the Medical History Log and Medication Log. The last recorded spirometric values in the participant's clinical records will also be documented.
- c.** Participant inclusion and exclusion criteria (Section 9.8) will be assessed, and ineligible patients excluded.
- d.** Participants will be allocated a myAIRVO 2 device and the device serial number will be recorded.
- e.** A training session on how to use myAIRVO 2 will be performed by the study investigator (Appendix 2). The participants' next of kin will be encouraged to be present at this session. Familiarization and acclimatization to the device and the therapy will also be conducted prior to leaving the hospital. Where possible any issues regarding the device or therapy will be addressed prior to discharge. The participant will also be given the myAIRVO 2 user manual and 'Quick guide sheet' to read prior to the home visit and a phone number to contact the investigator with any questions during business hours.
- f.** For participants on oxygen only: If possible, oxygen saturation testing on the participant's usual home oxygen flow will take place during the hospital admission. The participant will be placed on their home oxygen prescription while sitting at rest for at least 5 minutes. Should the participant's oxygen saturation levels on their prescribed oxygen be $<88\%$ or $\geq 95\%$ they will be withdrawn from the study and referred for review of their home oxygen prescription.
- g.** The investigator will confirm with the participant preferably on day of discharge, if they would still like to continue in the study. The Investigator will update the CRF, including the Medical Contact Log, Medical History Log, Medication Log and AE/SAE forms as required. The device plus consumables and any participant paperwork required for the study will be made available prior to discharge or taken to the patients home on the day of or day after being discharged from the hospital..

9.10.4. Post-discharge methods

- a.** A home visit will be made by an investigator on the day of or day after discharge. The investigator will:
- i. Ensure the equipment is set up correctly and reinforce the previous training on myAIRVO 2. (Appendix 1).
 - ii. Check participants will have the myAIRVO 2 user manual and the 'Patient summary sheet' as an easy reference for device use.
 - iii. Perform lung function tests using a spirometer (Jaegar pneumotac spirometer with J-Lab software) according to ATS/ERS Taskforce standards.^{10 11} Participants will not be required to withhold bronchodilator medication prior to testing. The drug, dose and time of the last administration prior to spirometry will be recorded. This will inform COPD severity of participants and baseline lung function measurements.
- b.** Participants on domiciliary oxygen will have oxygen saturations recorded on simple nasal prongs according to their existing prescription. NHF therapy will then be initiated and oxygen will be titrated through myAIRVO 2 to determine the flow of oxygen delivery required to achieve the same oxygen saturation level (Section 9.10.04).

c. myAIRVO 2 devices will electronically record data on the date and time the device was used. Should participants change the flow of their myAIRVO 2 device (participants without domiciliary oxygen only) or alter the temperature, they will be asked to document this in their diary.

d. On the 3rd, 7th, 14th and 21st and 28th day post discharge the investigator will contact the participant by phone. Participants will be asked:

- i. If they are having any problems using myAIRVO 2.
- ii. If they have needed to return to the hospital, the reason and length of their hospital visit. These details will be checked against hospital records. In addition, they will be asked if they have needed to visit their GP or other allied health care practitioners and the reason. The Investigator will complete the CRF and the medical history log, concomitant medications log, medical contact log, adverse event/ serious adverse event forms as required.

e. On the 31st day post discharge an investigator will perform a home visit or the participant will visit the study investigator at their clinic office.

- i. When the investigator contacts the participant on day 28th day post discharge they will confirm with the participant the home /office visit time on the 31st day post discharge and that their last period of myAIRVO 2 use is to commence on day 30 (the day before the home/office visit).
- ii. At the home/office visit the NHF therapy Questionnaire will be administered.
- iii. Participants will be asked whether they have had any hospital admissions and the length and cause for any admissions. These details will be checked against hospital inpatient records. In addition they will be asked if they have visited their GP or other allied health care practitioners. The Investigator will complete the CRF and the medical history log, concomitant medications log, medical contact log, adverse event/ serious adverse event forms as required.
- iv. Lung function will be performed using a spirometer (Jaegar pneumotac spirometer with J-Lab software) according to ATS/ERS Taskforce standards.^{10 11} Participants will not be required to withhold bronchodilator medication prior to testing. The drug, dose and time of the last administration prior to spirometry will be recorded. This will inform if lung function has improved during the study.
- v. The myAIRVO 2 device and associated equipment will be collected from the participant.

9.10.5. myAIRVO 2 domiciliary oxygen assessment and prescription

a. The participant will have their prescribed domiciliary oxygen flow rate recorded.

b. Oxygen saturation levels will be measured (Point A) by oximetry after at least 5 minutes at rest using standard nasal prongs with oxygen administered according to their prescription (Flow A). Should the participant's oxygen saturation levels be <88% or ≥95% they will be withdrawn from the study and referred for review of their home oxygen prescription.

c. NHF therapy will then be administered to the participant by myAIRVO 2 set at a flow rate of 25L/minute with supplemental oxygen delivered at Flow A for at least 5 minutes whilst the participant is at rest. Oxygen saturation levels will then be recorded.

d. While myAIRVO 2 is delivering 25L/min flow, oxygen will be titrated via the device by 0.5L/min every 5 minutes until the oxygen saturation levels measured at Point A (i.e. with the portable oximetry probe after sitting at rest for at least 5 minutes using standard nasal prongs with oxygen administered at Flow A) are equivalent. This flow rate will be used for supplemental oxygen delivered during NHF therapy via myAIRVO 2 throughout the study period.

e. An explanation will be given to the participant in respect to the risks and symptoms of hyperoxia, hypoxia, and hypercapnea, how to use myAIRVO 2 with correct oxygen flow rates, and how to change the oxygen flow between myAIRVO 2 and their standard nasal prongs (if required). They will also be provided with the “Quick guide sheet’ specific to patients on domiciliary oxygen.

f. If there is any clinical concern, the participant will be withdrawn from the study at the Investigator’s discretion. This may include, but is not limited to, concern regarding ability to maintain oxygen saturations within a safe range, the participant’s ability to understand the risks and symptoms of hypercapnia and hypoxia, and the participant’s ability to administer oxygen safely within the prescribed regimen.

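### The day-31 visit has no stated question or record check for ED visits without admission, so ED visits after the last phone call may be under-captured

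*Combined protocol and SAP*

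**What the plan says.** Objective 5 (section 8.2) includes ED visit rates among the clinical outcomes to be estimated for the planned randomized trial. Section 9.4 lists as a secondary outcome "Proportion of participants with at least one ED visit within 30 days of discharge", together with the reasons for ED visits, their number and the time to the first. Its footnote defines the event: "An ED visit is counted if the patient went to ED for assessment and was not subsequently admitted to a hospital ward".

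Section 9.10.4 collects these data in two ways.

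- **Phone calls (item d).** "On the 3rd, 7th, 14th and 21st and 28th day post discharge the investigator will contact the participant by phone". Participants are asked "If they have needed to return to the hospital, the reason and length of their hospital visit", and then: "These details will be checked against hospital records".
- **Day-31 visit (item e.iii).** "Participants will be asked whether they have had any hospital admissions and the length and cause for any admissions". The check is narrower: "These details will be checked against hospital inpatient records". A further question follows: "In addition they will be asked if they have visited their GP or other allied health care practitioners". The investigator also completes the CRF, the medical contact log and the adverse event forms where needed.

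Section 9.13 lets a contact that falls outside the working week move by one day either way. Section 11.1 plans Poisson regression for the number of ED visits and Kaplan-Meier estimation for the time to the first.

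**The concern.** The last contact is the only one that covers the end of the 30-day window, and its wording is narrower than that of the calls before it. By the protocol's own definition a countable ED visit is not an admission. A question about admissions does not ask for it, and a check of admission details against inpatient records is not designed to find it. The GP and allied health question does not naturally extend to an ED either.

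The SAE route is not a back-up on hospitalisation grounds, because section 12.3 leaves an ED presentation without admission out of its definition of hospitalisation.

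At stake are the ED endpoints, numbered 9.4.19 to 9.4.21 in section 11.1. A participant whose first ED visit fell on day 29 or 30 and went unrecorded would be analysed as having had none. Any such error goes in one direction: it lowers the proportion and the count, and it turns a late first event into a censored time.

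**Working it through.** **1. The two contacts side by side**

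| | Calls, days 3 to 28 | Visit, day 31 |
|---|---|---|
| Hospital question | Any return to hospital | Admissions only |
| Record check | Hospital records | Inpatient records |
| Other question | GP or other allied health | GP or other allied health |
| Can the hospital question and check capture an ED visit without admission? | Yes | Not as written |

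**2. Length of the gap**

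The inputs are the call days (section 9.10.4, d), the 30-day window (section 9.4) and the one-day allowance (section 9.13).

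- Last call on day 28: days 29 and 30 are uncovered, plus the rest of day 28 after the call. 2/30 = 6.7%.
- Last call moved to day 29: 1/30 = 3.3%.
- Last call moved to day 27: 3/30 = 10%.
- Day-28 call not completed: the gap runs from the day-21 call, so days 22 to 30. 9/30 = 30%, for that participant only. The documents give no rate of missed calls.

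**3. Effect on the ED proportion**

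The plan gives no expected ED rate, so there is no figure of its own to reproduce here. The denominators come from section 11.2, whose arithmetic does reproduce: 80/(1 − 0.20) = 100.

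The assumptions are a constant hazard over 30 days, a true 30-day proportion p between 5% and 30%, and loss of every ED visit in a gap of g days. Then

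observed proportion = 1 − (1 − p)^((30 − g)/30).

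For g = 2 and p = 10%: 1 − 0.90^(28/30) = 9.4%. For g = 2 and p = 20%: 1 − 0.80^(28/30) = 18.8%.

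| True p | g = 1 | g = 2 | g = 3 |
|---|---|---|---|
| 5% | 4.8% | 4.7% | 4.5% |
| 10% | 9.7% | 9.4% | 9.0% |
| 20% | 19.4% | 18.8% | 18.2% |
| 30% | 29.2% | 28.3% | 27.5% |

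For a 2-day gap, the participants wrongly counted as having no ED visit number about 0.3 (p = 5%, n = 80) to 1.7 (p = 30%, n = 100). With a 3-day gap the most is about 2.5 (p = 30%, n = 100).

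**4. Comparison with sampling error**

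The approximate 95% half-width is 1.96 × √(p(1 − p)/n). At n = 80 it is 6.6 percentage points for p = 10% and 8.8 points for p = 20%. The corresponding 2-day shifts are about 0.6 and 1.2 points, roughly a tenth and a seventh of the half-width.

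**The case against.** The best defence is that the text does not show these visits being lost. At the day-31 visit the investigator also completes the CRF, the medical contact log and the adverse event forms. Section 12.3 requires non-serious adverse events to be reported to the sponsor as well, so an ED attendance for an exacerbation could reach the file by that route. Section 9.10.7 lists the CRFs, the contact log and a data collection SOP, none of which is reproduced in the document. An ED prompt on those forms can be neither confirmed nor excluded. This stands, and it limits the point to visits that may be missed. It does not remove the point, because the protocol text itself contains no ED prompt and no ED record check at the last contact.

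A reader might go further in three ways that the documents do not support.

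- **That capture is complete for admissions, so ED rates are biased against readmission rates.** Admissions also depend on participant report and a record check, and the plan does not say which hospitals' records are covered. Section 11.1 describes the two outcomes separately and plans no comparison.
- **That up to 30% of ED follow-up is lost.** That figure applies only to a participant whose day-28 call was not completed. Otherwise the calls cover 27 to 29 of the 30 days (90% to 97%).
- **That the share of days equals the bias.** The headline endpoint is at least one ED visit, so a late visit by someone already counted leaves it unchanged.

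It is also fair to say that this is an uncontrolled feasibility study with no pass/fail criteria (sections 9.2 and 11.3). No treatment contrast is distorted.

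**Conclusion.** The point holds as a low-severity mismatch between an endpoint definition and its final data-collection step. Followed as written, section 9.10.4 e.iii gives no stated prompt or record check for a countable ED visit after the last call, a period of 2 of 30 days (1 to 3 under the rescheduling allowance). Any resulting error lowers the ED endpoints.

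For a true 30-day proportion of 10% to 20%, the observed value would be about 9.4% to 18.8% with a 2-day gap. That rests on a constant hazard, on ED rates that are assumed because the plan gives none, and on the loss of every visit in the gap. The last assumption makes it an upper limit for a gap of that length under this model, since the logs and forms may recover some visits. The effect is small against sampling error at n = 80. The primary endpoint, electronically recorded device use, and the sample size of 100 are unaffected.

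**What to change.** In section 9.10.4 e.iii, replace the admissions-only question with the one used at the phone calls (any return to hospital), and name ED visits without admission explicitly. Widen the record check from inpatient records to hospital inpatient and ED records, and apply it to the full 30 days after discharge. Checking the whole period also covers a participant whose day-28 call was not completed. If the CRF or medical contact log already carries an ED prompt, align the protocol text with it.

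The cost is one extra question at an existing visit and a slightly wider record check. No visit or participant is added, and the analysis in section 11.1 does not change.
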